The stimulation of these nerves by the gekoTM device causes the muscles to contract isometrically and will not affect normal movement of the limb nor patient mobility. Contraction of the lower leg muscles will boost venous return, local blood circulation and help prevent venous thrombosis. The gekoTM device has ten stimulation levels to balance maximal effect of stimulation with patient comfort. The optimal stimulation level, which may vary between patients, is achieved when a stimulus results in a dorsi-flexion of the foot.

The gekoTM device is fully insulated by a protective moulding and there is no risk of shock. It has charge-balanced waveforms that yield no build-up of charge in the patient. Therefore, provided the device is used in accordance with the instructions for use galvanic effects such as electrical burns cannot occur. The device is powered by battery, and is thus totally isolated from the mains electricity supply. The primary lithium coin cell battery powering the device is removable for disposal.

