9.10 Recording of Device Usage

The participants randomised to the geko™ study group will be provided with a participant diary for the purpose to record the daily geko™ device usage.

10 Statistical Analysis

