Appendix 6: Participant Diary

Dear Participant,

Please use this sheet to keep a record of your geko™ use over the course of the study. If you are unable to use the geko™ device for any reason, please contact your doctor or research nurse as soon as possible. Please use the geko™ device daily as instructed. If you forget to use completely, record on this sheet that the geko™ device was not used. Do not try to squeeze in extra doses by using the geko™ device for longer periods the next day.

Participant ID - **xxxxx**

TVx - TVx					
Date dd/mm/yyyy	Time you switched on the geko™ device (use 24hour format or include am/pm)	Time you switched off the geko™ device (use 24hour format or include am/pm)	Device setting (Please circle the setting used)	Label	Any comments
		Device turned off by itself 	1 2 3 4 5 6 7 8 9 10	Please insert the label on geko™ device pouch here	
		Device turned off by itself 	1 2 3 4 5 6 7 8 9 10	Please insert the label on geko™ device pouch here	
		Device turned off by itself 	1 2 3 4 5 6 7 8 9 10	Please insert the label on geko™ device pouch here	
		Device turned off by itself 	1 2 3 4	Please insert the label on geko™ device pouch here	

			5 6 7 8 9 10		
		Device turned off by itself 	1 2 3 4 5 6 7 8 9 10	Please insert the label on geko™ device pouch here	
		Device turned off by itself 	1 2 3 4 5 6 7 8 9 10	Please insert the label on geko™ device pouch here	
		Device turned off by itself 	1 2 3 4 5 6 7 8 9 10	Please insert the label on geko™ device pouch here	

To be completed by the investigator

Date collected the completed diary –

Initials of the person collected –

Signature of the person collected –

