The VLU Efficacy Study has shown an un-expected number of patients who do not respond to the W-2 geko™ device. In the parent study, 24% of patients were found to be non-responders to stimulation by the device as evidenced by a lack of dorsiflexion, the involuntary movement of the lower leg / foot at the maximum tolerable device setting. This is in contrast to a study following orthopaedic patients after total knee replacement, where only 5% of patients were found not to respond to stimulation by the device (unpublished data).

It is thought that excessive oedema in the area of the geko™ device application site may be preventing neuromuscular stimulation in VLU patients in the parent study.

In this sub-study, the sub-set of non-responders from the parent study, instead of being excluded, may continue in the study and receive their standard care with the aim to reduce oedema during the Run-in Phase. Subjects will also be evaluated at the start of the Run-in Phase for their response to a higher out-put T-3 geko™ device and tested weekly through-out the Run-in Phase with both W-2 or variant and T-3 geko™ devices. At the end of the Run-in Phase and following re-evaluation of their response to the W-2 or variant geko™ device, responders to the W-2 or variant geko™ device will re-join the treatment phase of the main protocol. Non-responders will be excluded at this stage.

It is hoped the results from this sub-study will show a positive correlation between treatment of excessive leg oedema and response to neuromuscular stimulation by the W-2 or variant geko™ device in VLU patients previously identified as non-responders in the VLU Efficacy Study.

This may be of two fold benefit to these patients:

1. Addressing oedema may ameliorate complications associated with untreated and persistent oedema, which can impede wound healing by obstructing blood flow throughout the body and to the wound site resulting in hypoxia, a key factor known to limit wound healing (15)
2. Treatment of oedema may also facilitate neuromuscular stimulation by the W-2 or variant geko™ device thus increasing blood flow, circulation and delivery of oxygen to the wound site (17, 19, 20, 21)

Study Objectives

This sub-study seeks to determine whether oedema in the area of the W-2 geko™ or variant device application site prevents neuromuscular stimulation by the device.

Subject Population

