Subjects will be a sub-set of subjects enrolled in the parent study at selected sites, following the same Inclusion / Exclusion criteria as per Section 3 of the main protocol, but who **do not** respond to the W-2 or variant geko™ device i.e. subjects who do not have an involuntary movement (dorsiflexion) of the lower leg / foot at the maximum tolerable device setting without the compression bandaging in place. Subjects must also have evidence of oedema, as determined by the Venous Clinical Severity Score (see section 4.1 of main protocol and Castor EDC - step 13).

A total of 20 subjects may qualify for participation.

Obtaining a separate informed consent for participation in the sub-study is not required and a subject may withdraw their consent to participate in the sub-study at any time as per Section 5 of the main protocol.

The investigator can withdraw a subject from the sub-study, if in his or her clinical judgment, it is in the best interest of the subject or if the subject cannot comply with elements of the sub-study protocol that are critical for safety or necessary for the scientific integrity of the study. If the investigator withdraws a subject from the study, the investigators will explain the reason for withdrawing the subject.

Study Schedule

All sub-study visits will be conducted according to the same time frame outlined in the Study Schedule (Section 4) of the existing main protocol. A schematic picture of the sub-study flow is provided in Figure1.

Run-in Phase

[figure not shown]
During the Run-in Phase, subjects will be evaluated on a weekly basis and study assessments performed as follows, see also Table 1.

- Remove compression bandaging
- Confirm subject **does not** respond to the W-2 or variant geko™ device by absence of dorsiflexion an involuntary movement of muscles in the lower leg / foot at the maximum tolerable device setting If subject does not respond, test subject's response to the higher output T-3 device. Subject's **do not** need to exhibit a positive response to the T-3 geko™ device to continue in the sub-study (RV1 only). Note: It is important that the device is applied to clean dry skin. Prior to application of the device, skin should be washed with mild soapy water, rinsed and dried thoroughly. Do NOT apply moisturiser at the device fitting site
- Measure ABPI if a valid ABPI reading has not been taken within 8 weeks of RV1 (RV1only)

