At the first Treatment Phase (TV1), once compression bandaging has been removed, confirm subject's response to the W-2 or variant geko™ device by presence of involuntary movement of muscles (dorsiflexion) in the lower leg / foot at the maximum tolerable device setting. If the subject does not respond to the W-2 or variant device the subject should be exited from the study and an early termination eCRF completed in EDC.

Once a subject's continued eligibility has been confirmed, randomisation and assignment to study treatment will take place and the subject will re-join the Treatment Phase of the main protocol and assessments completed as per the main protocol from section 4.2 onwards. Statistical analysis will be carried out using the Student's t-test

Table 1. Run-in Phase: Schedule of Sub-Study Assessments (assessments in bold are sub-study specific)

Activity/Assessment	RV1	RV2	RV3	RV4	RV5/TV1
Informed consent	✓				
Remove compression bandaging and assess response to W-2 or variant geko™	✓ [∞]				
Asses response to T-3 geko™	✓ [∞]				
Ankle-Brachial Index (ABPI) if a valid ABPI reading has not been taken within 8 weeks of RV1	✓				
Confirmation of eligibility	✓				
Assessment of leg oedema	✓ [¥]				
Medical history	✓				
CWIS, EQ-5D-5L and assessments	✓				
Physical examination and BMI	✓				
Concomitant medications	✓	✓	✓	✓	✓
Assessment of compression bandaging	✓	✓	✓	✓	✓
Study ulcer history	✓				
Study ulcer pain (VAS) assessment	✓	✓	✓	✓	✓
Venous Clinical Severity Score	✓				✓
Assess for AEs		✓	✓	✓	✓
Study ulcer cleaning	✓	✓	✓	✓	✓
Study ulcer surrounding skin assessment	✓				
Study ulcer image(s)	✓ [⌘]				
Study ulcer debridement	✓ [§]				
Application of compression	✓ [¶]				
Assessment for AEs since signing ICF	✓	✓	✓	✓	✓
Scheduling of next visit	✓	✓	✓	✓	✓

[∞] Presence of involuntary movement (dorsiflexion) of muscles in the lower leg and dorsiflexion of the foot at the maximum tolerable device setting W-2 or variant and T-3 before addition of compression bandaging

[¥] Assess leg oedema using a tape measure to determine leg circumference at the level of the geko™ device application site. Using an indelible surgical pen, mark a reference point on the leg, to ensure weekly measurements are taken at the same place on the leg.

[§] Study ulcer debridement at Investigator's discretion. N.B All study ulcer measurements will be performed using the pre-debridement images.

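### In the Appendix 8 sub-study, a change from non-responder to responder mixes the level needed to move the foot with the level tolerated that day, and no text supplied asks for the setting to be recorded

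*Combined protocol and SAP*

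**What the plan says.** Appendix 8 asks whether oedema at the device site stops the device from stimulating the nerve. Its Subject Population section admits "subjects who do not have an involuntary movement (dorsiflexion) of the lower leg / foot at the maximum tolerable device setting", tested without bandages, who also have oedema on the Venous Clinical Severity Score. Up to 20 may take part.

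The Introduction has them "tested weekly through-out the Run-in Phase with both W-2 or variant and T-3 geko™ devices"; the T-3 is described as the higher-output device. In the Treatment Phase section, the TV1 test is again for movement "in the lower leg / foot at the maximum tolerable device setting. If the subject does not respond to the W-2 or variant device", the participant leaves the study. Those who do respond are randomised into the main trial. The footnote to the sub-study's Table 1 uses the same criterion.

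Section 1.4 says the "device has ten stimulation levels to balance maximal effect of stimulation with patient comfort".

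Oedema has its own weekly measure: tape circumference at the device site, at a marked point. The analysis is one sentence naming Student's t-test, without a variable or comparison.

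In the documents supplied, a device setting is recorded only in the participant diary (Appendix 6), which has a column headed "Device setting (Please circle the setting used)". Under section 9.10 the participants in the geko "study group will be provided with a participant diary for the purpose to record the daily" device use, so the diary starts after the run-in.

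**The concern.** The yes/no result depends on two quantities: the lowest level that moves the foot, and the highest level the participant accepts that day. The sub-study's hypothesis concerns only the first. The second can differ between visits for reasons unrelated to oedema, and it is not written down.

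Everyone enters as a non-responder, so any change can only be towards response. There is no group without oedema treatment in which to see how often the result changes anyway. Following the plan exactly would therefore leave its own question confounded by tolerance, and a setting not recorded at the visit cannot be recovered later.

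**Working it through.** **1. The two quantities.** Let N be the lowest level that moves the foot and T the highest level tolerated at a visit. Response means N ≤ T.

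- Entry at RV1 requires N1 > T1.
- Conversion at TV1 requires N2 ≤ T2.
- The oedema hypothesis is N2 < N1.

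Conversion also occurs with N unchanged whenever T1 < N ≤ T2. For example, N = 7 at both visits, T1 = 6 and T2 = 7 is a conversion with no change in the leg. Without T1 and T2, this looks the same as N falling from 7 to 6 with T = 6 throughout.

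**2. What circumference adds.**

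| | Responds at or below the RV1 tolerated level | Responds only above it |
|---|---|---|
| Leg shrank | fits the hypothesis | undetermined |
| Leg did not shrink | not explained by circumference | tolerance is sufficient |

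Circumference separates the rows. Only the setting separates the columns.

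**3. Direction of the error.** The analysis sentence leaves two readings open.

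- If conversions are counted, tolerance-only conversions are added to the count, so the apparent effect is inflated.
- If circumference change is compared between converters and non-converters, suppose a fraction f of converters are tolerance-only and have the same mean change as non-converters. If the true contrast is D, the expected observed contrast is (1 − f) × D. This is dilution, against the hypothesis.

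**4. Possible size.** The documents give no figure for this, so there is nothing to reproduce. The one anchor is the 24% non-response in the parent study (Appendix 8, Introduction). Everything else here is assumed. N is normal and unchanged over the run-in. T is normal at each visit with total SD s and within-person SD w, so the correlation between visits is 1 − w²/s². The mean of T rises by 0 or 1 level. The quantity wanted is P(N ≤ T2 given N > T1), from 2,000,000 simulated participants.

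*Model A:* N has mean 5 and SD 2; T has mean 7 and SD 2; no ceiling. Non-response at RV1 is P(Z > (7 − 5)/√(4 + 4)) = P(Z > 0.71) = 0.24.

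*Model B:* N has mean 4 and SD 6; T has mean 8.5 and SD 1.5; T is capped at level 10. Simulated non-response at RV1 is also 0.24.

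| Converting with N unchanged | w = 0.5 | w = 1.0 |
|---|---|---|
| A, no rise | 13% | 26% |
| A, one-level rise | 41% | 48% |
| B, no rise | 5% | 10% |
| B, one-level rise | 16% | 19% |

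The cap alone does not explain the gap: adding it to A changes its figures by less than one percentage point. The gap comes from how many participants need more than level 10. In A this is P(Z > (10 − 5)/2) = P(Z > 2.5) = 0.006. In B it is P(Z > (10 − 4)/6) = P(Z > 1) = 0.16, so about 0.16/0.24, or two thirds, of B's non-responders cannot be moved at any level.

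On 20 participants, no rise gives 0.05 × 20 = 1 to 0.26 × 20 = 5.2 conversions. A one-level rise gives 0.16 × 20 = 3.2 to 0.48 × 20 = 9.6.

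**The case against.** **Oedema is measured separately.** A reader might infer that anyone who tolerates a higher setting is counted as having recovered from oedema. The documents do not say so. That person is a responder who re-joins the main trial, and an unchanged leg would be visible in the circumference data. This part of the objection stands in full. What remains is the converter whose leg did shrink.

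**The plan defines no conversion rate.** This also stands. Under a circumference comparison the error works against the sponsor's hypothesis. But the analysis sentence excludes neither reading, and each gives a distorted answer.

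**The setting may be captured elsewhere.** The appendix refers to an electronic data capture system, its flow chart is not shown, and the fitting instructions were sent separately. The claim is therefore limited to the documents supplied.

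**The criterion has a purpose.** It matches main-trial exclusion criterion 10 and the RV1 check in section 4.1. As a test of whether the participant can use the device, it is coherent. The objection is only to using it unaided as evidence about oedema.

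**Nothing shows that tolerance rises with repeated testing.** Correct; that is an assumption, and weekly tests with a higher-output device only make it plausible. Ordinary visit-to-visit variation is enough to produce some conversions. A participant already at level 10 at RV1 cannot convert through tolerance.

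**Conclusion.** The concern holds in a limited form. RV1 non-response and TV1 response are each judged at that day's tolerable setting, and the documents supplied do not call for the setting to be recorded. A conversion therefore cannot be assigned to a lower level needed rather than a higher level tolerated, and circumference resolves this only in part.

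The size is not known. The ranges of 5-26% without a rise in tolerance and 16-48% with a one-level rise come from two arbitrary models that share only the 24% non-response. They show that the effect could be small or large in 20 participants; they are not estimates. They also assume that sub-study participants resemble the parent-study non-responders behind the 24%.

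A reader might also infer that the main trial's primary result is compromised. Nothing here supports that: the issue concerns how the sub-study result is interpreted, and the fix leaves entry to the main trial as written. Severity is minor.

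**What to change.** At each response test already being done with the W-2 or variant and with the T-3, record two numbers: the highest setting tolerated and the lowest setting that produced the movement (or that none did). If the eCRF already holds these, say so in Appendix 8.

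Add to the Appendix 8 analysis text:

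- response at or below the maximum setting tolerated at RV1 with the same device, reported alongside the change in circumference;
- conversions seen only above that setting, reported separately.

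The rule for re-joining the main trial is unchanged. The cost is two recorded numbers per test and a short addition to the analysis text. The reported conversion rate may be lower.
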